8.4.5.2. Exposure During Breastfeeding

An EDB occurs if:

- A female participant is found to be breastfeeding while receiving or after discontinuing study intervention.
- A female nonparticipant is found to be breastfeeding while being exposed or having been exposed to study intervention (ie, environmental exposure). An example of environmental EDB is a female family member or healthcare provider who reports that she is breastfeeding after having been exposed to the study intervention by ingestion, inhalation, or skin contact.

The investigator must report EDB to Pfizer Safety within 24 hours of the investigator's awareness, irrespective of whether an SAE has occurred. The information must be reported using the PSSA. When EDB occurs in the setting of environmental exposure, the exposure information does not pertain to the participant enrolled in the study, so the information is not recorded on a CRF. However, a copy of the completed report is maintained in the investigator site file.

An EDB report is not created when a Pfizer drug specifically approved for use in breastfeeding women (eg, vitamins) is administered in accordance with authorized use. However, if the infant experiences an SAE associated with such a drug, the SAE is reported together with the EDB.

8.4.5.3. Occupational Exposure

The investigator must report any instance of occupational exposure to Pfizer Safety within 24 hours of the investigator's awareness using the PSSA regardless of whether there is an associated SAE. Since the information about the occupational exposure does not pertain to a participant enrolled in the study, the information is not recorded on a CRF; however, a copy of the completed report is maintained in the investigator site file.

8.4.6. Cardiovascular and Death Events

Not applicable.

8.4.7. Disease-Related Events and/or Disease-Related Outcomes Not Qualifying as AEs or SAEs

Not applicable.

8.4.8. Adverse Events of Special Interest

Not applicable.

8.4.8.1. Lack of Efficacy

This section is not applicable because efficacy is not expected in the study population.

8.4.9. Medical Device Deficiencies

Medical devices being provided for use in this study are those listed in Section [6.1.2](#). In order to fulfill regulatory reporting obligations worldwide, the investigator is responsible for the detection and documentation of events meeting the definitions of device deficiency that occur during the study with such devices.

The definition of a medical device deficiency can be found in [Appendix 9](#).

Note: AEs and/or SAEs that are associated with a medical device deficiency will follow the same processes as other AEs or SAEs, as outlined in Section [8.4.1](#) through [8.4.4](#) and [Appendix 3](#) of the protocol.

8.4.9.1. Time Period for Detecting Medical Device Deficiencies

Medical device deficiencies that result in an incident will be detected, documented, and reported during all periods of the study in which the medical device is used.

Importantly, reportable device deficiencies are not limited to problems with the device itself but also include incorrect or improper use of the device and even intentional misuse, etc.

If the investigator learns of any device deficiency at any time after a participant has been discharged from the study, and such deficiency is considered reasonably related to a medical device provided for the study, the investigator will promptly notify the sponsor.

Refer to Section [10.9.4](#) for instructions for documenting and reporting medical device deficiencies.

8.4.9.2. Regulatory Reporting Requirements for Device Deficiencies

The investigator will promptly report all device deficiencies occurring with any medical device provided for use in the study in order for the sponsor to fulfill the legal responsibility to notify appropriate regulatory authorities and other entities about certain safety information relating to medical devices being used in clinical studies.

The investigator, or responsible person according to local requirements (eg, the head of the medical institution), will comply with the applicable local regulatory requirements relating to the reporting of device deficiencies to the IRB/EC.

Note: There are additional reporting obligations for medical device deficiencies that are potentially related to SAEs (ie, an SADE) that must fulfill the legal responsibility to notify

appropriate regulatory authorities and other entities about certain safety information relating to medical devices being used in clinical studies.

- Any device deficiency that is associated with an SAE must be reported to the sponsor within 24 hours after the investigator determines that the event meets the definition of a device deficiency.
- The sponsor shall review all device deficiencies and determine and document in writing whether they could have led to an SAE. These shall be reported to the regulatory authorities and IRBs/ECs as required by national regulations.

8.4.10. Medication Errors

Medication errors may result from the administration or consumption of the study intervention by the wrong participant, or at the wrong time, or at the wrong dosage strength.

Medication errors are recorded and reported as follows:

Recorded on the Medication Error Page of the CRF	Recorded on the Adverse Event Page of the CRF	Reported on the PSSA to Pfizer Safety Within 24 Hours of Awareness
All (regardless of whether associated with an AE)	Any AE or SAE associated with the medication error	Only if associated with an SAE

Medication errors include:

- Medication errors involving participant exposure to the study intervention;
- Potential medication errors or uses outside of what is foreseen in the protocol that do or do not involve the study participant.

Whether or not the medication error is accompanied by an AE, as determined by the investigator, such medication errors occurring to a study participant are recorded on the medication error page of the CRF, which is a specific version of the AE page and, if applicable, any associated serious and nonserious AE(s), are recorded on the AE page of the CRF.

In the event of a medication dosing error, the sponsor should be notified within 24 hours.

Medication errors should be reported to Pfizer Safety within 24 hours on a PSSA **only when associated with an SAE**.

8.5. Pharmacokinetics

Venous blood samples of approximately 4 mL, to provide approximately 1.5 mL plasma, will be collected for measurement of plasma concentrations of zavege pant as specified in the

SoA. Prior to centrifugation of blood samples collected at the time points specified in the **SoA, Table 2**, a 500 µL portion of the PK blood sample will be aliquoted and used to determine the blood-to-plasma ratio of zavegeptan. Determining the blood-to-plasma ratio will be crucial for converting the dried blood concentrations collected using Tasso-M20 to their equivalent plasma concentrations for adequate comparison between the 2 methods. For Tasso sampling, approximately 100 µL of blood will be collected from participants using the Tasso-M20 devices, while for Tasso-Plus, approximately 300-500 µL of blood will be collected to provide approximately 150 - 200 µL serum into appropriately labeled tubes for the measurement of zavegeptan concentration as specified in the **SoA, Table 2**. Of note, both Tasso and venous PK samples will be collected at the same time. Instructions for the collection and handling of biological samples will be provided in the laboratory manual or by the sponsor. The actual date and time (24-hour clock time) of each sample will be recorded.

All efforts will be made to obtain the samples at the exact nominal time relative to dosing. Collection of samples up to and including 10 hours after dose administration that are obtained within 10% of the nominal time relative to dosing (eg, within 6 minutes of a 60-minute sample) will not be captured as a protocol deviation, as long as the exact time of the collection is noted on the source document and the CRF. Collection of samples more than 10 hours after dose administration that are obtained \leq 1 hour away from the nominal time relative to dosing will not be captured as a protocol deviation, as long as the exact time of the collection is noted on the source document and the CRF. This protocol deviation window does not apply to samples to be collected more than 10 hours after dose administration at outpatient/follow-up visits with visit windows.

Samples will be used to evaluate the PK of zavegeptan. Samples collected for analyses of zavegeptan concentration may also be used to evaluate safety or efficacy aspects related to concerns arising during or after the study, for metabolite identification and/or evaluation of the bioanalytical method. The data may be used for other internal exploratory purposes. The exploratory results may not be reported in the CSR.

Genetic analyses will not be performed on the collected PK samples unless consent for this was included in the informed consent. Participant confidentiality will be maintained.

Samples collected for measurement of zavegeptan concentrations will be analyzed using a validated analytical method in compliance with applicable SOPs.

The PK samples must be processed and shipped as indicated in the instructions provided to the investigator site to maintain sample integrity. Any deviations from the PK sample handling procedure (eg, sample collection and processing steps, interim storage or shipping conditions), including any actions taken, must be documented and reported to the sponsor. On a case-by-case basis, the sponsor may make a determination as to whether sample integrity has been compromised.

Any changes in the timing or addition of time points for any planned study assessments must be documented and approved by the relevant study team member and then archived in the sponsor and site study files, but will not constitute a protocol amendment. The IRB/EC will

be informed of any safety issues that require alteration of the safety monitoring scheme or amendment of the ICD.

8.6. Genetics

8.6.1. Specified Genetics

Specified genetic analyses are not evaluated in this study.

8.6.2. Retained Research Samples for Genetics

A 4-mL blood sample optimized for DNA isolation Prep D1 will be collected according to the [SoA](#), as local regulations and IRBs/ECs allow.

Retained Research Samples may be used for research related to the study intervention. Genes and other analytes (eg, proteins, RNA, nondrug metabolites) may be studied using the retained samples.

See [Appendix 5](#) for information regarding genetic research. Details on processes for collection and shipment of these samples can be found in the laboratory manual and supporting documentation.

8.7. Biomarkers

Biomarkers are not evaluated in this study.

8.8. Immunogenicity Assessments

Immunogenicity assessments are not included in this study.

8.9. Health Economics

Health economics/medical resource utilization and health economics parameters are not evaluated in this study.

9. STATISTICAL CONSIDERATIONS

Detailed methodology for summary and statistical analyses of the data collected in this study is outlined here and further detailed in the SAP, which will be maintained by the sponsor. The SAP may modify what is outlined in the protocol where appropriate; however, any major modifications of the primary endpoint definitions or their analyses will also be reflected in a protocol amendment.

9.1. Statistical Hypotheses

There is no statistical hypothesis for this study.

9.2. Analysis Sets

For purposes of analysis, the following analysis sets are defined:

Participant Analysis Set	Description
Enrolled	“Enrolled” means a participant’s, or their legally authorized representative’s, agreement to participate in a clinical study following completion of the informed consent process and assignment to study intervention. A participant will be considered enrolled if the informed consent is not withdrawn prior to participating in any study activity. Potential participants who are screened for the purpose of determining eligibility for the study, but do not participate in the study, are not considered enrolled, unless otherwise specified by the protocol.
PK Concentration Analysis Set	All enrolled participants who receive 1 single IN dose of zavegeptan and provide at least 1 evaluable plasma concentration.
PK Parameter Analysis Set	All enrolled participants who receive 1 single IN dose of zavegeptan and provide at least 1 evaluable PK parameters of interest.
Taste Assessment Set	All participants who receive at least 1 single IN dose of zavegeptan and complete the Taste Assessment Questionnaire
Safety Analysis Set	All participants who take at least 1 dose of study intervention. Participants will be analyzed according to the product they actually receive.

9.3. Statistical Analyses

The SAP will be developed and finalized before any analyses are performed and will describe the analyses and procedures for accounting for missing, unused, and spurious data. This section is a summary of the planned statistical analyses of the primary and secondary endpoints.

9.3.1. General Considerations

No formal statistical tests will be performed. Descriptive summaries will be provided for all endpoints by each blood collection method. For the taste assessment in this study, the data used in the analysis will be transcribed and rescaled to a score from 0 to 100 from the raw measurements on the questionnaire. The sensory attributes (overall liking, bitterness, tongue/mouth burn, throat burn, sour taste, salty taste, and sweet taste) from the taste questionnaires ([Appendix 11](#)) will be listed and descriptively summarized by study intervention (zavegeptan alone vs zavegeptan + butterscotch candy) and time points.

PFIZER CONFIDENTIAL

CT02-GSOP Clinical Pharmacology Protocol Template (14 April 2023)

Page 62

Summary statistics (mean and 90% CI) will be calculated for the various questions. Radar plots for each of 4 time points, summarizing all attributes for each intervention will be generated. Boxplots of each attribute will be plotted against the time points. More details will be provided in the SAP.

9.3.2. Pharmacokinetic Analysis

9.3.2.1. Derivation of PK Parameters

Zavege pant PK parameters from samples collected using Tasso and venous phlebotomy will be derived from the concentration-time profile using non-compartmental methods, as detailed in [Table 3](#). Actual PK sampling times will be used in the derivation of PK parameters. In the case that actual PK sampling times are not available, nominal PK sampling time will be used in the derivation of PK parameters.

Table 3. Plasma PK Parameters for Protocol C5301022

Parameter	Definition	Method of Determination
C_{\max}	Maximum plasma concentration	Observed directly from data
AUC_{last}	Area under the plasma concentration-time profile from time 0 to the time of the last quantifiable concentration (C_{last})	Linear/Log trapezoidal method
AUC_{inf}^a	Area under the plasma concentration-time profile from time 0 extrapolated to infinite time	$AUC_{\text{last}} + (C_{\text{last}}/k_{\text{el}})$, where C_{last} is the predicted plasma concentration at the last quantifiable time point estimated from the log-linear regression analysis
T_{\max}	Time for C_{\max}	Observed directly from data as time of first occurrence
$t_{1/2}^a$	Terminal half-life	$\log_2(2)/k_{\text{el}}$, where k_{el} is the terminal phase rate constant calculated by a linear regression of the log-linear concentration-time curve
CL/F^a	Apparent clearance	Dose/ AUC_{inf}
V_z/F^a	Apparent volume of distribution	Dose/ $(AUC_{\text{inf}} \times k_{\text{el}})$

a. If data permits.

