2.3.1. Risk Assessment

Potential Risk of Clinical Significance	Summary of Data/Rationale for Risk	Mitigation Strategy
Study Intervention Zavegeptan		
Hypersensitivity reactions	Hypersensitivity reactions including facial swelling and urticaria have occurred with zavegeptan.	Site staff and participants are instructed throughout protocol and ICD to immediately report all AEs post-dosing for further management instructions.
AEs associated with IN administration, such as dysgeusia, throat irritation, nasal congestion and nasal discomfort.	The potential risks are based on AEs reported in studies of zavegeptan IN administration, and the majority have been of mild to moderate intensity.	Eligibility criteria have been selected to ensure that only appropriate participants are included in the study (see Section 5.1). Nasal inspection will be conducted on Day -1 (to exclude participants with mucosal erythema, congestion, septal defects etc), and 24 h (\pm 30 min) postdose per the SoA. AEs and clinical laboratory results will be monitored on an ongoing basis.
Study Procedures		
The study intervention will be administered intranasally via a liquid spray device.	The IN administration could be affected by some human and operational factors, such as the way of handling the devices and the way of inhalation and exhalation. These may lead to higher variabilities in PK data.	Enhanced site training and participant education in terms of the study intervention administration. For all the study participants, all attempts would be made for study intervention administration performed by no more than 3 study staff members to minimize variability in device handling.
Relatively intensive PK sampling and narrow time window within 1 hour post dose.	Risk of PK sample collection outside the required time window might be higher.	Enhance site communication and training. Actual PK sampling times will be used in the derivation of PK parameters.
Other		
Atypical PK sampling methodology (Tasso devices)	Risk of improper collection procedure that could lead to compromised sample(s)	Enhanced site communication and training on Tasso device collection and handling procedures

PFIZER CONFIDENTIAL

CT02-GSOP Clinical Pharmacology Protocol Template (14 April 2023)

Page 30

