4. STUDY DESIGN

4.1. Overall Design

This is a single-center, Phase 1, non-randomized, open-label, 2-period study in healthy participants to primarily evaluate the correlation of zavegeptan concentration from samples

PFIZER CONFIDENTIAL

CT02-GSOP Clinical Pharmacology Protocol Template (14 April 2023)

Page 31

collected using Tasso Devices (Tasso-Plus and Tasso-M20) compared to standard venous phlebotomy. This study consists of two periods which will include approximately 14 participants.

In period 1, 50% (n=7) of participants will use Tasso-Plus, while the other 50% (n=7) will use Tasso-M20. All 14 participants will have 6 PK samples collected using the assigned Tasso device simultaneously with collecting venous blood samples at the following time points, 30 minutes, 1, 2-, 4-, 8-, and 12-hour postdose, as described in the [SoA, Table 2](#). In addition, taste assessments will be performed at time intervals of 1 (immediately after dosing), 5, 10 and 20 minutes after zavegeptan IN administration. Also, if feasible, 4 Japanese participants will be enrolled among those 14 participants to evaluate the PK and safety of zavegeptan IN in Japanese vs. non-Japanese participants. For Japanese participants, a total of 12 venous blood samples will be collected at the following time points, 0, 15 minutes, 30 minutes, 1, 1.5-, 2-, 3-, 4-, 6-, 8-, 12-, and 24-hour (refer to [SoA, Table 2](#)).

In period 2, a butterscotch candy will be given 5 minutes before administering the zavegeptan IN study intervention. Taste assessment will also be performed after zavegeptan IN administration with a butterscotch candy in period 2. For taste assessment, each participant will record the sensory attributes at timed intervals of 1 (immediately after dosing), 5, 10 and 20 minutes after zavegeptan administration in each period.

Healthy participants will be screened within 28 days prior to the first administration of the study intervention to confirm that they meet the participant selection criteria for the study. Eligible participants will be admitted to the CRU on Day -1 and will be confined in the CRU until Discharge on Day 3 ([SoA](#)), approximately 24 hours after the second dose. Enrolled participants will receive a single IN dose of zavegeptan 10 mg (0.1 mL) in each period. PK venous blood samples as well as Tasso PK sampling, using Tasso-Plus and Tasso-M20, will be collected at specified intervals as per [SoA \(Table 2\)](#) for PK assessments.

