3. ENDPOINTS AND BASELINE VARIABLES: DEFINITIONS AND CONVENTIONS

3.1. Primary Endpoints

3.1.1. Zavegepant PK Concentrations

Venous blood and Tasso PK samples will be collected according to the SoA given in the protocol. For each individual, blood to plasma (B/P) ratios will be calculated by dividing concurrent (i.e. Day 1, 1 hour and 8 hour post-dose) whole blood zavegepant concentrations with the plasma zavegepant concentrations. The plasma equivalent zavegepant concentration by microsampling using the Tasso-M20 will be calculated by dividing with the individual B/P ratio. For the Tasso-Plus, normalization of the zavegepant concentration is not needed.

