6.1.2. Zavegepant PK Parameters

The PK parameters of zavegepant will be listed and summarized descriptively for each collection method (Tasso-Plus, Tasso-M20 and venous phlebotomy), and by race (non-Japanese and Japanese), as data permits for the PK Parameter Analysis Set. Each zavegepant PK parameter will be summarized including the set of summary statistics as specified in Table 3.

For AUC_{last} , AUC_{inf} , and C_{max} , box and whisker plots for individual participant parameters will be constructed for each collection method and overlaid with geometric means.

Table 3. PK Parameters to be Summarized Descriptively by Collection Method and Race

Parameter	Summary Statistics
AUC_{inf} , AUC_{last} , C_{max} , CL/F , V_z/F	N, arithmetic mean, median, SD, %CV, minimum, maximum, geometric mean and geometric %CV
T_{max} , T_{last}	N, median, minimum, maximum
$t_{1/2}$	N, arithmetic mean, median, SD, %CV, minimum, maximum

Supporting data from the estimation of $t_{1/2}$ and AUC_{inf} will be listed by collection method and by race: terminal phase rate constant (k_{el}); goodness of fit statistic from the log-linear regression (r^2); the percent of AUC_{inf} based on extrapolation ($AUC_{extrap}\%$); and the first, last, and number of time points used in the estimation of k_{el} . This data may be included in the clinical study report.

For the Tasso vs. Venous comparison, natural log-transformed zavegepant AUC_{inf} (if data permit), AUC_{last} and C_{max} will be analyzed using a mixed effect model with blood collection method as fixed effect and participant as random effect. Estimates of the adjusted mean differences (Test – Reference) and corresponding 90% CIs will be obtained from the model with Venous as the Reference group and Tasso-M20 (or Tasso-Plus) as the Test group. The adjusted mean differences and 90% CIs for the differences will be exponentiated to estimate the adjusted geometric means ratio (Test/Reference) and 90% CIs for the ratios.

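### The Tasso/venous ratios of AUClast and Cmax compare values built from each method's own usable samples, so a Tasso sample missing at 12 h or 0.5 h pulls the ratio below 1 with no device difference

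*Protocol*

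**What the plan says.** Protocol 9.3.2.1, repeated in SAP 3.1.2, states that "PK parameters from samples collected using Tasso and venous phlebotomy will be derived from the concentration-time profile using non-compartmental methods". In the parameter table of each section, AUClast covers the interval "from time 0 to the time of the last quantifiable concentration" and Cmax is "Observed directly from data". Each method therefore has its own end time and its own peak.

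All participants have paired Tasso and venous samples at "30 minutes, 1, 2-, 4-, 8-, and 12-hour postdose" (Protocol 4.1). SAP 6.1.2 compares the methods on the log scale for AUClast, Cmax and, where it can be estimated, AUCinf; each of these "will be analyzed using a mixed effect model with blood collection method as fixed effect and participant as random effect". Venous sampling is the reference, and the output is a geometric mean ratio (GMR) with a 90% CI.

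SAP 5.3.1 handles problem samples one at a time. Values below the limit of quantification (BLQ) are set to zero in presentations, missing values stay missing, and anomalous values may be excluded by judgement. It does not mention the paired partner. Protocol 2.3.1 lists compromised Tasso samples as a risk, and Protocol 8.5 adds: "On a case-by-case basis, the sponsor may make a determination as to whether sample integrity has been compromised".

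**The concern.** The model is meant to isolate the effect of the collection method within a participant. That requires both values to describe the same stretch of the curve. If the Tasso profile ends at 8 h and the venous profile at 12 h, the AUClast ratio compares 0-8 h with 0-12 h. If the 0.5 h Tasso draw is unusable, the Tasso Cmax becomes the 1 h value, while the venous Cmax can still come from 0.5 h. The participant random effect cannot remove this, because the within-participant contrast is itself distorted.

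The losses need not be symmetric. Protocol 8.5 describes about 100 µL of dried blood for Tasso-M20, 150-200 µL of serum for Tasso-Plus and about 1.5 mL of venous plasma, and these need not share a quantification limit. The M20 plasma-equivalent value "will be calculated by dividing with the individual B/P ratio" (SAP 3.1.1). A blood-to-plasma ratio below 1 would therefore raise the M20 limit in plasma-equivalent units, and a ratio above 1 would lower it.

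PK parameters are primary endpoints, and the study is meant to support Tasso sampling in children. A GMR below 1 would naturally be read as the device under-measuring.

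**Working it through.** **The plan's own figure.** Protocol 9.5 counts 7 participants × 6 pairs = 42 pairs per device, which reproduces. That count concerns paired concentrations. For AUClast and Cmax there are only 7 within-participant ratios per device. No power, alpha or margin is stated.

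**Inputs from the documents.** Sampling times are 0.5, 1, 2, 4, 8 and 12 h (Protocol 4.1). Tmax is 0.54 h, elimination half-life about 3 h and effective half-life 6.55 h (Protocol 4.2). AUC uses the linear/log trapezoidal rule (Protocol 9.3.2.1).

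**Assumptions.** True Tasso and venous concentrations are identical, so the correct ratio is 1. Concentration is zero at time 0. The two half-lives serve as a range for the decay rate. A device's GMR is taken as the exponential of the mean log ratio over its seven users.

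**Step 1: 12 h Tasso sample missing, simple decay.** With C(t) = exp(−k(t − 0.5)) and k = ln 2 / half-life, the trapezoidal AUC to time T is 0.25 + (1 − C(T))/k.

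- 3 h: k = 0.2310, C(8) = 0.1768, C(12) = 0.0702. AUC(0-8) = 3.813 and AUC(0-12) = 4.274, so the ratio is 0.892.
- 6.55 h: k = 0.1058, C(8) = 0.4522, C(12) = 0.2961. AUC(0-8) = 5.427 and AUC(0-12) = 6.901, so the ratio is 0.786.

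**Step 2: a curve with the protocol's Tmax.** Take C(t) proportional to exp(−kt) − exp(−ka·t), with ka solving ln(ka/k)/(ka − k) = 0.54. This gives ka = 6.374 (3 h) and 8.150 (6.55 h).

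| Unusable Tasso sample | AUClast ratio, 3 h / 6.55 h | Cmax ratio, 3 h / 6.55 h |
|---|---|---|
| 12 h | 0.891 / 0.786 | 1.000 / 1.000 |
| 0.5 h | 0.940 / 0.963 | 0.932 / 0.965 |
| one of 1, 2, 4 or 8 h | 0.996 to 1.000 | 1.000 |

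The Cmax ratio is C(1)/C(0.5): 0.7920/0.8496 = 0.932 and 0.8993/0.9315 = 0.965.

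**Step 3: effect on the device GMR.** With m of 7 users affected, the GMR is (ratio)^(m/7).

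| m of 7 | AUClast GMR, 12 h missing (3 h / 6.55 h) | Cmax GMR, 0.5 h missing (3 h / 6.55 h) |
|---|---|---|
| 1 | 0.984 / 0.966 | 0.990 / 0.995 |
| 2 | 0.968 / 0.934 | 0.980 / 0.990 |
| 3 | 0.952 / 0.902 | 0.970 / 0.985 |

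**Step 4: random loss.** A simulation of 4000 runs assumed 10% sample error and independent Tasso losses of 5, 10 or 20%. The own-sample derivation gave mean AUClast GMRs of 0.990, 0.975 and 0.937 (3 h) or 0.985, 0.966 and 0.918 (6.55 h). Cmax GMRs were 0.994, 0.985 and 0.964, or 0.994, 0.989 and 0.974. Using only time points usable in both methods gave 0.999 to 1.001 throughout.

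**The case against.** The strongest reply is that the main bridging evidence does not depend on this model. SAP 6.1.1 plans correlation and Bland-Altman analyses of paired concentrations, where an unusable Tasso value simply removes its pair. AUCinf is less exposed: on the idealised curve a lost tail leaves it unchanged. No hypothesis or margin is attached to the GMR. All of this stands, and it limits the harm to a misleading estimate and interval. A reader might infer that the study's bridging conclusion fails or that a test would go wrong. The documents do not support either.

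The truncation would also be visible. SAP 6.1.2 summarises Tlast by collection method, and SAP 6.1.1 gives the number of concentrations above the limit by method and time, with individual plots overlaying the methods. These displays would reveal a short Tasso profile but would not correct the ratio.

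SAP 5.3.1 excludes a parameter estimate known to be biased, which could cover a truncated AUC. The clause is discretionary, its example is vomiting, and using it would discard that parameter for the participant when only seven use each device. It is a partial safeguard.

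Finally, a BLQ Tasso value beside a measurable venous value is information about device or assay sensitivity. Matching alone would hide it: BLQ at 12 h in all seven users would still give a ratio of 1. This is correct, and the remedy must allow for it.

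**Conclusion.** The point holds as a specific weakness in the SAP 6.1.2 comparison. Unequal availability of the 12 h or 0.5 h sample enters the GMR as an apparent device effect, and nothing in either document prevents it. Per affected participant the AUClast ratio is about 0.89 to 0.79 and the Cmax ratio about 0.93 to 0.97. For AUClast, one affected user in seven costs about 2-3% and three cost about 5-10%.

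Three stronger readings go too far:

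- All seven users of a device losing the 12 h value would give 0.89 or 0.79, but the lower figure is implausible as a BLQ result. It treats the effective half-life as a decay rate, and on that curve about 30% of peak remains at 12 h, against about 7% at 3 h.
- A Cmax ratio of 0.89 follows only from pure decay after 0.5 h. The protocol's Tmax supports the milder figures above.
- The protocol names compromised Tasso samples as a risk, to be mitigated by training. It does not predict a loss rate.

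Loss rates, quantification limits and blood-to-plasma ratios are not given, so how often this would occur is unknown. The sizes rest on the assumed curves.

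**What to change.** In SAP 6.1.2, for the Tasso versus venous model only, derive AUC and Cmax in each participant from the time points usable in both members of the pair. End both AUCs at the last such common time, and label the results as matched-time values. The label matters because, without the 0.5 h pair, the modelled maximum may no longer be the usual Cmax. Restricting the analysis to the six shared nominal times would not be enough, since a loss can occur at any of them.

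Keep each method's own-sample AUClast and Cmax in the descriptive tables. Add a table of lost and BLQ samples, counted separately by method and time point, including Tasso BLQ results with a quantifiable venous partner. A real sensitivity limit then stays visible.

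The cost is SAP wording, one extra non-compartmental run and one table. No visit, sample or participant changes. The downside is that the venous partner of an unusable Tasso sample goes unused in the ratio, and the AUC may cover a shorter interval.
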